5.2.2. Exclusion Criteria

Deviations from exclusion criteria are not allowed because they can potentially jeopardize the scientific integrity of the study, regulatory acceptability or subject safety. Therefore, adherence to the criteria as specified in the protocol is essential.

Subjects meeting any of the following criteria must not be enrolled in the study:

1. Systemic anti-tumor-therapy within 14 days, or plasmapheresis within 7 days prior to the first dose of study drug.
2. Use of an investigational drug within 14 days or five half-lives, whichever is shorter, preceding the first dose of study drug. Prior treatment with a monoclonal antibody within 30 days of receiving the first dose of study drug.
3. History of an allogeneic stem cell transplant. Subjects with a history of an autologous stem cell transplant are NOT excluded if they meet Inclusion Criterion #5.
4. Presence of active renal condition (infection, requirement for dialysis or any other condition that could affect subject's safety). Subjects with isolated proteinuria resulting from MM are eligible, provided they fulfil criteria given in Table 14.
5. Evidence of active mucosal or internal bleeding.
6. Any major surgery within the last four weeks.
7. Any serious and/or unstable pre-existing medical, psychiatric disorder, or other conditions (including lab abnormalities) that could interfere with subject's safety, obtaining informed consent or compliance to the study procedures.
8. Known active infection requiring antibiotic treatment.
9. Evidence of severe or uncontrolled systemic diseases (e.g., unstable or uncompensated respiratory, hepatic, renal or cardiac disease).
10. Subjects with previous or concurrent malignancies are allowed only if the second tumor is not contributing to the subject's illness. The subject must not be receiving

active therapy, other than hormonal therapy for this disease and the disease must be considered medically stable for at least 2 years.

11. Evidence of cardiovascular risk including any of the following:
 - a. QTc interval \geq 470 msec.
 - b. Evidence of current clinically significant uncontrolled arrhythmias;
 - a. including clinically significant ECG abnormalities including 2nd degree (Type II) or 3rd degree atrioventricular (AV) block.
 - c. History of myocardial infarction, acute coronary syndromes (including unstable angina), coronary angioplasty, or stenting or bypass grafting within six months of Screening.
 - d. Class III or IV heart failure as defined by the New York Heart Association functional classification system ([Appendix 4](#))
 - e. Uncontrolled hypertension
 - f. Subjects with intra-cardiac defibrillators or permanent pacemakers;
 - g. Abnormal cardiac valve morphology (\geq Grade 2) documented by echocardiogram (subjects with grade 1 abnormalities [i.e., mild regurgitation/stenosis] can be entered on study). Subjects with moderate valvular thickening should not be entered on study.
12. Known immediate or delayed hypersensitivity reaction or idiosyncrasy to drugs chemically related to GSK2857916 or any of the components of the study treatment.
13. Pregnant or lactating female.
14. Known HIV infection.
15. Subjects with positive test for Hepatitis B surface (HBS-Ag) or Hepatitis B core (HBc)antigen
16. Subjects with positive test for hepatitis C (HCV) infection are excluded regardless of viral load. If hepatitis C antibody test is positive, a confirmatory polymerase chain reaction (PCR) or recombinant immunoblot assay (RIBA) test should be performed. If the RIBA test is negative, subject is eligible for this trial.
17. Current active liver or biliary disease (with the exception of Gilbert's syndrome or asymptomatic gallstones, liver metastases or otherwise stable chronic liver disease per investigator's assessment).
18. Current corneal disease or a history of corneal disease.

6. COMPLETION OR WITHDRAWAL OF SUBJECTS

6.1. Screen and Baseline Failures

Data for screen and baseline failures will be collected in source documentation at the site but will not be transmitted to GSK.

6.2. Subject Completion Criteria

For Part 1 (dose-escalation phase), a completed subject is one who has completed at least 1 cycle of study treatment and an End of Study Visit without events causing them to withdraw or discontinue from the study for reasons listed in Section 6.3. For Part 2 (expansion cohort), a completed subject is one who has received at least one dose of study treatment without events causing them to withdraw or discontinue study treatment for reasons listed in Section 6.3 and completed an End of Study Visit.

A participant will be considered to have completed the study if he or she has received at least one dose of the study treatment and, has died before the end of the study, has not been lost to follow-up, or has not withdrawn consent from study participation.

6.3. Permanent Discontinuation from Study Treatment

Subjects will receive study treatment until disease progression, death or unacceptable toxicity, including meeting stopping criteria for significant toxicity as outlined in Section 3.10 and other relevant safety management guidelines outlined in the protocol, or until a maximum of 16 treatment cycles. In addition, study treatment may be permanently discontinued for any of the following reasons:

- deviation(s) from the protocol
- request of the subject or proxy (withdrawal of consent by subject or proxy)
- investigator's discretion
- a dose delay of >14 days unless the investigator or GSK Medical Monitor agree that subject derives benefit and that further treatment benefits will outweigh the risks. Exceptions apply to nephrotoxicity as outlined in Section 3.10.2
- intercurrent illness that prevents further administration of study treatment(s)
- subject is lost to follow-up
- study is closed or terminated
- subject completes maximum number of treatment cycles per protocol
- The primary reason study treatment was permanently discontinued must be documented in the subject's medical records and electronic case report form (eCRF)

If the subject voluntarily discontinues from treatment due to toxicity, 'adverse event (AE)' will be recorded as the primary reason for permanent discontinuation on the eCRF.

Once a subject has permanently discontinued from study treatment, the subject will not be allowed to be retreated.

All subjects who discontinue from study treatment will have safety assessments at the time of discontinuation and during post-study treatment follow-up as specified in Time and Events Tables (see Section 7.1).

6.4. Subject Withdrawal

Should a subject fail to attend the clinic for a required study visit, the site should attempt to contact the subject and re-schedule the missed visit as soon as possible. The site should also counsel the subject on the importance of maintaining the assigned visit schedule and ascertain whether or not the subject wishes to and/or should continue in the study based on previous non-compliance. In cases where the subject does not return for the rescheduled visit or cannot be reached to reschedule the missed visit, the site should make every effort to regain contact with the subject (3 telephone calls and if necessary a certified letter to the subject's last known mailing address) so that they can appropriately be withdrawn from the study. These contact attempts should be documented in the subject's medical record. Should the subject continue to be unreachable, then and only then will he/she be considered to have withdrawn from the study with a primary reason of "Lost to Follow-up". For all other subjects withdrawing from the study, an alternative reason for discontinuation should be recorded in the eCRF.

6.5. Study Completion

A study will be considered completed, having met the study objectives, when the last subject has received their last dose of study medication and completed the End of Study visit.

Per the EU Clinical Trial Directive, the end of the study is defined as the last subject's last visit.

6.6. Treatment after the End of Study

The investigator is responsible for ensuring that consideration has been given for the post-study care of the subject's medical condition whether or not GSK is providing specific post-study treatment.

Subjects' survival and status of post-study treatment will be documented via medical charts analysis at 3 months following the last dose of study drug.

7. STUDY ASSESSMENTS AND PROCEDURES

A signed, written informed consent form must be obtained from the subject prior to any study-specific procedures or assessments being performed.

The timing of each assessment is listed in the Time and Events Tables (Section 7.1). The timing and number of the planned study assessments may be altered during the course of the study based on newly available data (e.g. to obtain data closer to the time of peak plasma concentrations) to ensure appropriate monitoring for the following assessments: safety, pharmacokinetic (PK), pharmacodynamic (PD)/biomarker or other assessments. The change in timing or addition of time points for any of the planned study assessments listed above must be approved and documented by GSK, but this will not constitute a protocol amendment. The institutional review board (IRB) or ethics committee (EC) will be informed of any safety issues that require alteration of the safety monitoring scheme. The maximum amount of blood collected in Screening and during the first Cycle 1 from

each subject for the Dose Escalation and for the Dose Expansion is no more than 162 ml of blood (See [Appendix 10](#)).

Whenever vital signs, 12-lead electrocardiograms (ECGs) and blood draws are scheduled for the same nominal time, the assessments should occur in the following order: 12-lead ECG, vital signs, blood draws. The timing of the assessments should allow the blood draw to occur at the exact nominal time. Detailed procedures for obtaining each assessment are provided in the SPM.

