20. Collect cytokines at predose (within 30 minutes prior to SOI) and EOI (\pm 5 min) (even when infusion is interrupted or halted) to assess allergic reaction
21. All ADA samples will be collected prior to each infusion
22. PK samples to be taken (in all subjects) for both GSK2857916 and cys-mcMMAF measurement: C1D1 at predose (within 30 minutes prior to SOI), 0.5 h after the start of the infusion, at EOI (just before EOI), 1 h after EOI (\pm 5 min), 3 h after EOI (\pm 5 min), 8 h after EOI (\pm 15 min), and 24h after EOI (\pm 1 h) (Day 2); C1D8 at predose (within 30 minutes prior to SOI), and at EOI (just before EOI); C1D15 at predose (within 30 minutes prior to SOI) and at EOI (just before EOI); C2D1 at predose (within 30 minutes prior to SOI), at EOI (just before EOI); C3D1 at predose (within 30 minutes prior to SOI) and at EOI (just before EOI).
23. Collect 1 PK sample at each subject's final visit.

24. Pre-specified amounts of urine will be collected for PK analysis from the 24 hour urine collection at Screening, C2D1, C4D1, C7D1, C10D1, C13D1, and C16D1. Refer to Section 7.4.2 for details.
25. Study drug administration ± 1 day window only.
26. Prophylaxis with prednisolone phosphate 1% or dexamethasone 0.1% 1 drop QID x 4 days starting 1 day prior to treatment
27. Record subject's survival status and whether subsequent treatment for disease was given. Subject does not need to come in for visit.

Abbreviations:

ADA = Antibody Drug Antibody; ALP = alkaline phosphatase; BCVA = best corrected visual acuity; BNP = B-type natriuretic peptide; C1D1 = Cycle 1 Day 1, etc.; cfDNA = Circulating free DNA; CK = creatinine kinase; CRP = C-reactive protein; EM = extramedullary; EOI = End of Infusion; FLC = free light chain; PD = Pharmacodynamics; PK = Pharmacokinetics; QID = 4 times a day; SOI = start of infusion; SPEP = serum protein electrophoresis; UPEP = urine protein electrophoresis

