7.4. Pharmacokinetics

7.4.1. Blood Sample Collection for Pharmacokinetics

Blood samples of approximately 5 mL for pharmacokinetic (PK) analysis of GSK2857916 (ADC and total antibody) and cys-mcMMAF will be collected at the time points indicated in the Time and Events Tables (Section 7.1). Each PK sample should be collected as close as possible to the planned time relative to the dose (i.e., time zero) administered to the subject on PK days. The actual date and time of each blood sample collection will be recorded.

Details on PK blood sample collection, processing, storage and shipping procedures are provided in the Study Procedures Manual (SPM). Blood volumes for PK samples are outlined in [Appendix 10](#) (Section 16.9).

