16.8. Appendix 9: Urine Protein Creatinine (UPC) Ratio Clinical meaning of UPC

There is a good correlation between the ratio of protein concentration to creatinine concentration in a random urine sample and the amount of protein excreted over 24 hours. Creatinine excretion is fairly constant throughout the day regardless of changes in urine flow rate.

Normal protein excretion is <150 mg/24 hours and is similar for men and women.

Men excrete 20 mg to 25 mg of creatinine/kg of body weight/day.

Women excrete 15 mg to 20 mg of creatinine/kg of body weight/day.

Calculating UPC

UPC ratio = Urine protein (mg/dL) / Urine creatinine (mg/dL).

UPC ratio \approx equivalent to grams of protein excreted in urine over 24 hrs.

Example: Patient has a urine protein = 90 mg/dL and urine creatinine = 30 mg/dL.

UPC ratio = (90 mg/dL) / (30 mg/dL) = 3

The calculated UPC ratio is 3, which correlates to roughly 3 g protein excretion in a 24-hour period.

Units for UPC ratio

Note: To calculate UPC, protein and creatinine concentrations must be expressed in the same units (mg/dL, g/L, or $\mu\text{mol/L}$). If, for example, protein concentration is expressed in mg/dL and creatinine concentration is expressed in $\mu\text{mol/L}$, conversion of one of the concentration values is required. Conversion factors are:

From	To	Conversion Factor
Conventional Units: mg/dL	SI Units: $\mu\text{mol/L}$	Multiply by 88.4
SI Units: $\mu\text{mol/L}$	Conventional Units: mg/dL	Divide 88.4

References:

NKF: NKF KDOQI Guidelines [Internet]. National Kidney Foundation; nd. KDOQI Clinical Practice Guidelines for Chronic Kidney Disease: Evaluation, Classification, and Stratification. Available from http://www.kidney.org/professionals/KDOQI/guidelines_ckd/p5_lab_g5.htm

16.9. Appendix 10: Blood Requirements**16.9.1. Blood Requirements for All Lab Tests, Except PK****16.9.1.1. Dose Escalation: Every 3 Weeks for Multiple Myeloma**

Test Sample	Sample Volume	Screening	Cycle 1	Each Subsequent Cycle
Hematology	5 ml	5 ml	10-15 ml	5 ml
Chemistry	5 ml	5 ml	15-20 ml	5 ml
Coagulation	5 ml	5 ml	10-15 ml	5 ml
SPEP	6 ml	6 ml		6 ml
CRP	1 ml	1 ml		1 ml
B2 Microglobulin	1 ml	1 ml		1 ml
Kappa, lambda free LC, FLC	1 ml	1 ml		1 ml
IgG, IgA, IgM	6 ml	6 ml		6 ml
cfDNA	10 ml	10 ml		
Cytokines	3 ml		6 ml	6 ml
HBV/HCV	3 ml	3 ml		

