16.9.2. Blood Requirements for PK

PK Schedule	Sample Volume	Cycle 1	Cycle 2	Cycle 3	Cycle 5	Total Volume
Escalation Every 3 Weeks	5 ml	60 ml	10 ml	10 ml		80 ml
Escalation Weekly	5 ml	80 ml	10ml	10 ml		100 ml
Expansion Every 3 Weeks MM	5 ml	20 ml	20 ml	20 ml	20 ml	80 ml
Expansion Weekly MM	5 ml	20 ml	10 ml	10 ml	10 ml	50 ml
Expansion Every 3 Weeks Lymphomas	5 ml	40 ml	20 ml	20 ml	10 ml	90 ml
Expansion Weekly Lymphomas	5 ml	40 ml	20 ml	20 ml	10 ml	90 ml

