16.9.3. Total Blood Requirements

Schedule	Screening	Cycle 1	Each Subsequent Cycle
Escalation Every 3 Weeks MM	59.5 ml	51.5-66.5 ml	45.5-51.5 ml
Escalation Weekly MM	43.5 ml	73.5-88.5 ml	48.5-54.5 ml
Expansion Every 3 Weeks MM	43.5 ml	68.5-83.5 ml	48.5-54.5 ml
Expansion Weekly MM	43.5 ml	68.5-83.5 ml	48.5-59.5 ml
Expansion Every 3 Weeks Lymphomas	36.5 ml	67.5-82.5 ml	40.5-47.5 ml
Expansion Weekly Lymphomas	36.5 ml	74.5-89.5 ml	40.5-51.5 ml

The Study Procedures Manual will be updated with new information if changes in blood volumes are required.

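### The 162 mL maximum for blood drawn in Screening plus Cycle 1 does not reconcile with the sampling schedule or with Appendix 10, and weekly escalation exceeds it across its whole range

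*Protocol*

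**What the plan says.** - **Section 7** gives one maximum for every schedule. The amount collected in Screening and during Cycle 1 from "each subject for the Dose Escalation and for the Dose Expansion is no more than 162 ml of blood", with Appendix 10 as the reference.
- **Section 7.4.1** sets the PK volume: "Blood samples of approximately 5 mL for pharmacokinetic (PK) analysis of GSK2857916 (ADC and total antibody) and cys-mcMMAF". One sample of about 5 mL therefore serves both analytes.
- **Time and Events footnotes** list the PK draws. For weekly escalation (7.1.1.2, footnote 22) the text begins "PK samples to be taken (in all subjects) for both GSK2857916 and cys-mcMMAF measurement: C1D1 at predose" and continues through seven draws to 24 hours, then two each on Days 8 and 15.
- **Appendix 10, 16.9.1** tabulates volumes under the heading "Blood Requirements for All Lab Tests, Except PK".
- **Appendix 10, 16.9.2** gives PK volumes separately; its "Escalation Weekly" row shows 80 mL in Cycle 1.
- **Appendix 10, 16.9.3** is headed "Total Blood Requirements". Its rows, for example "Escalation Every 3 Weeks MM 59.5 ml 51.5-66.5 ml" and "Escalation Weekly MM 43.5 ml 73.5-88.5 ml", are the same figures as the non-PK totals in 16.9.1.

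**The concern.** A table presented as a total leaves out a category that the table just before it puts at 20 to 80 mL in Cycle 1. Once PK is included, the maximum in Section 7 is no longer a maximum on several schedules. A site on weekly escalation cannot follow both the sampling schedule and the limit. The limit is operative text that describes the burden on each subject, so it should be a figure the schedule can meet.

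**Working it through.** **Trying to reproduce 162.** The limit is a maximum, so I use the upper end of each Cycle 1 range. The largest Screening + Cycle 1 sum over the six schedules is:
- without PK, as in 16.9.3: 43.5 + 88.5 = 132 mL;
- with the 16.9.2 PK volume: 132 + 80 = 212 mL;
- with scheduled PK samples at 5 mL: 132 + 11 × 5 = 187 mL.

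Taking 3 mL per PK sample gives 132 + 33 = 165 mL. None of these is 162.

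**PK volume in Cycle 1: schedule against 16.9.2.**

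| Schedule | Source of count | Samples | × 5 mL | 16.9.2 |
|---|---|---|---|---|
| Escalation 3-weekly | 7.1.1.1, fn 21 | 7+1+1 = 9 | 45 | 60 |
| Escalation weekly | 7.1.1.2, fn 22 | 7+2+2 = 11 | 55 | 80 |
| Expansion 3-weekly MM | 7.1.2.1, fn 24 | 2 | 10 | 20 |
| Expansion weekly MM | 7.1.2.2, fn 22 | 4+2+2 = 8 | 40 | 20 |
| Expansion 3-weekly lymphoma | 7.1.2.3, fn 18 | 4 | 20 | 40 |
| Expansion weekly lymphoma | 7.1.2.4, fn 17 | 4+2+2 = 8 | 40 | 40 |

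Five of six disagree, in both directions.

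**Screening + Cycle 1 + PK (mL).** The formula is printed Screening + printed Cycle 1 (lower to upper) + PK.

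| Schedule | Non-PK | + scheduled PK | + 16.9.2 PK |
|---|---|---|---|
| Escalation 3-weekly | 59.5 + 51.5–66.5 = 111–126 | 156–171 | 171–186 |
| Escalation weekly | 43.5 + 73.5–88.5 = 117–132 | 172–187 | 197–212 |
| Expansion 3-weekly MM | 43.5 + 68.5–83.5 = 112–127 | 122–137 | 132–147 |
| Expansion weekly MM | 43.5 + 68.5–83.5 = 112–127 | 152–167 | 132–147 |
| Expansion 3-weekly lymphoma | 36.5 + 67.5–82.5 = 104–119 | 124–139 | 144–159 |
| Expansion weekly lymphoma | 36.5 + 74.5–89.5 = 111–126 | 151–166 | 151–166 |

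At the maximum, four of six exceed 162 mL with scheduled PK, and three of six with the 16.9.2 volumes. Weekly escalation exceeds at its minimum on either basis.

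**Errors inside 16.9.1.** The Cycle 1 items for weekly MM expansion add to 82.5 mL at the upper end, not the printed 83.5. Those for weekly lymphoma add to 86.5 mL, not 89.5. With these sums the maxima become 43.5 + 82.5 + 40 = 166 and 36.5 + 86.5 + 40 = 163 mL.

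Some rows also undercount the schedule. In weekly escalation the Time and Events table needs seven cytokine draws in Cycle 1 (predose and end of infusion on Days 1, 8 and 15, plus Day 2), which is 7 × 3 = 21 mL against 6 listed. It needs two ADA draws (6 against 3 mL) and two TBNK draws (12 against 6 mL). The shortfall is 15 + 3 + 6 = 24 mL, so the maximum is 187 + 24 = 211 mL.

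The same recount of all scheduled Cycle 1 draws gives maxima, in table order, of 174, 211, 143, 202, 145 and 184 mL, and minima 15 mL lower: 159, 196, 128, 187, 130 and 169 mL. The same four schedules exceed 162 mL.

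**The case against.** Several limits on this point are fair and stand.

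- On the printed totals, three of the four schedules exceed only toward the upper end; their minima are 156, 152 and 151 mL. The 15 mL spread is the repeat of Day 1 haematology, chemistry and coagulation, which footnote 6 waives if they were done within 72 hours before the first dose. The totals also include a 2 mL pregnancy test that applies only to women of childbearing potential. Weekly lymphoma on the itemised sum, without that test, is 161 mL and complies.
- PK samples are approximately 5 mL, so an excess of 4 or 5 mL is close to rounding.
- Three of the four schedules are weekly, and weekly dosing is optional in this protocol.
- If the limit is read as applying to each period separately, weekly escalation Cycle 1 is 88.5 + 55 = 143.5 mL with scheduled PK, which is under it. That reading strains a sentence that joins Screening and Cycle 1 under one figure. It also fails with the 16.9.2 PK volume (168.5 mL) and on the full recount (112.5 + 55 = 167.5 mL).
- 16.9.3 lets the Study Procedures Manual update blood volumes, but that does not correct the figure in Section 7.

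Stronger readings go beyond the documents. A reader might infer that 162 is too low *because* PK was left out. If so, 162 should match the non-PK totals, and their maximum is 132. A reader might quote an excess of 31% (212 mL), but that uses the 16.9.2 PK volume, which the schedule contradicts (80 against 55 mL). The recount lands near it, at 211 mL, only because a 25 mL PK overstatement and a 24 mL undercount elsewhere nearly cancel. A reader might link the excess to the haemoglobin entry limit of 8.0 g/dL, but the documents give no safety threshold for blood volume. What subjects were told cannot be assessed, because consent pages are not shown.

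**Conclusion.** The stated maximum is wrong as written. With scheduled PK samples added to the printed non-PK totals, weekly escalation runs from 172 to 187 mL, which is 10 to 25 mL over 162 (25/162 = 15% at most). The maxima on 3-weekly escalation, weekly MM expansion and weekly lymphoma are 171, 167 and 166 mL (163 mL for the last with its itemised sum). On that basis these three exceed only at the upper end. Both 3-weekly expansion schedules comply on every basis tried.

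This rests on one sample of 5 mL per PK time point, as in Section 7.4.1, and on reading the limit as Screening and Cycle 1 together. The count of four depends on the Time and Events schedule; the PK table in 16.9.2 would give three. It would be too strong to say that the study breaks its limit by design on four schedules, since only weekly escalation does so whichever PK source is added to the printed totals. No endpoint, analysis or dosing decision depends on the figure. It is a per-subject maximum in operative text that is inexpensive to correct, and it should be corrected.

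**What to change.** 1. Recompute all of Appendix 10, both 16.9.1 and 16.9.2, from the Time and Events tables and their footnotes. Correcting 16.9.2 alone would leave the cytokine, ADA and TBNK undercounts and the two addition errors in place.
2. Add PK to every row of 16.9.3 so that it is a total.
3. Replace the single figure in Section 7 with a maximum per schedule taken from that recount, about 211 mL for weekly escalation, and say whether it covers Screening and Cycle 1 together.
4. Carry the corrected figure to any subject-facing text that quotes the maximum.

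The cost is corrected tables and a less favourable stated figure. Sampling does not change.
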